### **10.49 Output 49 Most Common Adverse Event with Incidence $\geq$ 5% by Preferred Term**

Programing notes:

1. Analysis population: Safety
2. Template ID: AET08
3. Program name: T\_AE\_PT\_P5
4. Display only by preferred term, not by SOC

### **10.50 Output 50 Most Common Grade 3, 4, 5 Adverse Event with Incidence $\geq$ 5% by Preferred Term**

Programing notes:

1. Analysis population: Safety
2. Template ID: AET08
3. Program name: T\_AE345\_PT\_P5

## 10.51 Output 51 Duration from First Study Treatment Date to Onset of Peripheral Neuropathy

	Treatment Group 1 (N=nn)	Treatment Group 2 (N=nn)
Duration from first study treatment to onset of PN (months)		
n	nnn	nnn
Mean (SD)	xx.x (xx.x)	xx.x (xx.x)
Median	xx.x	xx.x
Min-max	xx-xx	xx-xx
Duration from first study treatment to onset of grade 2 or higher PN (months)		
n	nnn	nnn
Mean (SD)	xx.x (xx.x)	xx.x (xx.x)
Median	xx.x	xx.x
Min-max	xx-xx	xx-xx

### Programing notes:

1. Analysis population: Safety
2. Template ID: NA
3. Program name: T\_DUR\_PN
4. Use univariate variable analysis
5. **This output is applied to studies with polatuzumab**

## 10.52 Output 52 Listing of Deaths

Center/ Patient ID	Age/Sex/Race	Date of First Study Drug Administration	Day of Last Study Drug Administration	Day of Death	Associated SAE Preferred Term	Autopsy Performed?	Cause of Death
[REDACTED]			12	62	Myocardial infarction	Yes	xxxxxx
			36	37	Ischemic Stroke	No	xxxxxx

### Programming notes:

1. Analysis population: Safety
2. Template ID: AEL04
3. Program name: L\_DD

### 10.53 Output 53 Deaths

	Treatment Group 1 (N=nn)	Treatment Group 2 (N=nn)
All deaths	xx (xx.x%)	xx (xx.x%)
Adverse Events	xx (xx.x%)	xx (xx.x%)
Disease Progression	xx (xx.x%)	xx (xx.x%)
No. of deaths during treatment		
Cause of death		
Adverse Events	xx (xx.x%)	xx (xx.x%)
Disease Progression	xx (xx.x%)	xx (xx.x%)
No. of deaths during follow up		
Cause of death		
Adverse Events	xx (xx.x%)	xx (xx.x%)
Disease Progression	xx (xx.x%)	xx (xx.x%)
No. of deaths during survival follow up		
Cause of death		
Adverse Events	xx (xx.x%)	xx (xx.x%)
Disease Progression	xx (xx.x%)	xx (xx.x%)

Deaths during the treatment are those occurred within 28 days after last study drug.

Programming notes:

1. Analysis population: ITT
2. Program name: T\_DD
3. CRF: AE and Study Completion/Early Discontinuation

### 10.54 Output 54 Laboratory Test Results Shift Table - Highest NCI CTCAE Grade Post-Baseline

Hemoglobin g/L (Low)	From	Status at Baseline						Total	Missing
		0	1	2	3	4			
To									
0		13(xx%)	0 (xx%)	1(xx%)	0	0	14	0	
1		58(xx%)	63(xx%)	4(xx%)	0	0	125	0	
2		39(xx%)	105(xx%)	28(xx%)	0	0	172	0	
3		14(xx%)	23(xx%)	13(xx%)	0	0	50	0	
4		3(xx%)	5(xx%)	0(xx%)	0	0	8	0	
Total		127(100%)	196(100%)	46(100%)	0	0	360	0	
Missing		6	6	0	0	0	12	0	

NCI CTCAE = National Cancer Institute Common Terminology Criteria for Adverse Events.

“n” denotes the number of patients with baseline and post-baseline lab data within this time interval. For a patient with multiple post-baseline lab abnormalities, the highest (worst) grade of these abnormalities for the given lab test is reported.

Programing notes:

1. Analysis population: Safety
2. Template ID: LBT14
3. Program name: T\_LB\_SHIFT
4. Use **EXT\_NCICTC4** for NCI-CTCAE Grades
5. Include all hematology and chemistry lab parameters split into 2 separate outputs.

## 10.55 Output 55 Neutrophil Count Recovery

	Treatment Group 1 (N=nn)	Treatment Group 2 (N=nn)
ANC < 1.0 × 10  /L at EOT/EOI*		
Yes	xx (xx.x%)	xx (xx.x%)
No	xx (xx.x%)	xx (xx.x%)
n	xxx	xxx
ANC Recovery** within 3 months of follow up		
Yes	xx (xx.x%)	xx (xx.x%)
No	xx (xx.x%)	xx (xx.x%)
n	xxx	xxx
ANC Recovery** within 6 to 9 months of follow up		
Yes	xx (xx.x%)	xx (xx.x%)
No	xx (xx.x%)	xx (xx.x%)
n	xxx	xxx
ANC Recovery** within 9 to 12 months of follow up		
Yes	xx (xx.x%)	xx (xx.x%)
No	xx (xx.x%)	xx (xx.x%)
n	xxx	xxx
A ANC Recovery** after 12 months of follow up		
Yes	xx (xx.x%)	xx (xx.x%)
No	xx (xx.x%)	xx (xx.x%)
n	xxx	xxx

\*\* Neutrophil recovery is defined as ANC ≥ 1.0 × 10^9/L, given ANC was collected after the patient received his last dose of antibody, and ANC < 1.0 × 10^9/L the last previous visit before EOT/EOI. Where no ANC value occurs at the last drug intake, the next valid ANC assessment was taken.

Percentages are based on the number of patients with ANC < 1.0 × 10^9/L at the last previous visit before EOT/EOI.

Programing notes:

1. Analysis population: Safety
2. Program name: T\_LB\_ANC

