### **5.1.1.3 Neutropenia**

Grade 3 or 4 neutropenia, including febrile neutropenia, has been reported with obinutuzumab administration. Neutropenia resolved spontaneously or with use of hematopoietic growth factors. Patients who experience Grade 3 or 4 neutropenia should be closely monitored until neutrophil values return to at least Grade 2. Cases of late-onset neutropenia (ANC < 1000 cells/ $\mu$ L occurring  $\geq$  28 days after obinutuzumab treatment has been completed or stopped) or prolonged neutropenia (ANC < 1000 cells/ $\mu$ L) that does not resolve after 28 days without obinutuzumab treatment have also been reported. Prophylactic treatment with antibiotics should be administered as per standard practice. The use of G-CSF is allowed for treatment of neutropenia in this study. Guidelines for *treatment and* primary prophylaxis with G-CSF are provided in Section 4.4.1.

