### **6.2.2 Selected AEs and AE of Special Interest (AESI)**

Selected AE and AESI were defined based on the clinical experience with study treatment components that represent an IMP. Also anticipated potentially overlapping toxicities as specified in respective study protocols need to be taken into account.

Definitions for selected AE and AESI are provided in subsequent tables.

Selected AE Category	Definition	BO29563	BO29562	BO29561	BH29812	BH39147	GO29833	GO29834
Thrombocytopenia	SMQ "HAEMATOPOIETIC THROMBOCYTOPENIA narrow" (20000031n)	x	x	x	x	x	x	x
Hepatitis B reactivation/newly occurring	PT 'HEPATITIS B'	x	x	x	x	x	x	x
Cardiac AE	SOC "CARDIAC DISORDERS"	x	x	x	x	x	x	x
Infusion Related Reaction (IRR)	PT 'INFUSION RELATED REACTION' and related to at least one component of study treatment and event occurred within 24 hours or during infusion and tickbox 'Systemic Infusion Reaction' ticked (This definition was applied in BO29563- study lead BioStats/SPA please check if this is valid for your study)	x	x	x	x	x	x	x
Infections	SOC 'INFECTIONS AND INFESTATIONS'	x	x	x	x	x	x	x
Neutropenia	Roche Standard AEGT "NEUTROPENIA AND ASSOCIATED COMPLICATIONS" (for BO29561-3: including late onset and prolonged neutropenia) (SMQ Haematopoietic leukopenia narrow for GO29833/834)	x	x	x	x	x	x	x

Selected AE Category	Definition	BO29563	BO29562	BO29561	BH29812	BH39147	GO29833	GO29834
Prolonged neutropenia	Initial ANC < 1.0 × 10  /L that is still present 28 days after treatment with GA101				x	x		
Late onset Neutropenia	ANC < 1.0 × 10  /L occurring ≥ 28 days after ga101 infusion has been completed/stopped				x	x		
Gastrointestinal perforation	SMQ "GASTROINTESTINAL PERFORATION" (20000107 narrow).	x	x	x	x	x	x	x
Peripheral Neuropathy (motor/and or sensory)	SMQ Peripheral neuropathy wide			x			x	x
Dose Limiting Toxicity	CRF tickbox				x			
Drug-drug interactions	Single PT		x					

AE of Special Interest	Definition	BO29563	BO29562	BO29561	BH29812	BH39147	GO29833	GO29834
Drug induced liver injury	<del>Respective tickbox for AESI on CRF page ticked</del>				x	x	x	x
Suspected transmission of infectious agent	<del>Respective tickbox for AESI on CRF page ticked</del>				x	x	x	x
Grade 4 thrombocytopenia	SMQ "HAEMATOPOIETIC THROMBOCYTOPENIA narrow" (20000031n)						x	
Grade ≥ 3 infection	SOC						x	
Grade ≥ 3 thrombocytopenia or Grade 2 thrombocytopenia if associated with hemorrhage/bleeding	?				x	x		
Grade ≥ 2 diarrhea	?				x	x		

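### SAP Output 55 has no row for neutrophil recovery between 3 and 6 months, and no hematology is scheduled after EOM or EOC to find late-onset neutropenia or confirm recovery

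*SAP*

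**What the plan says.** **Recovery table.** SAP Output 55 has four recovery rows: "within 3 months of follow up", "within 6 to 9 months of follow up", a row for 9 to 12 months, and a row for later than 12 months. Each has its own Yes, No and n. Percentages are based on patients whose neutrophil count (ANC) was below 1.0 × 10^9/L at the last visit before end of treatment or induction. The SAP update log has no entry for Output 55.

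**Recovery rule.** SAP 6.4.3 accepts a count of 1.0 × 10^9/L or more after the last antibody dose as recovery only if the next visit also shows at least 1.0. A missing next visit means not recovered.

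**Late-onset neutropenia.** Protocol 5.1.1.3 lists it among the obinutuzumab risks ("Cases of late-onset neutropenia"), and protocol 5.2.4 makes it a selected adverse event. SAP 6.2.2 defines it as ANC below 1.0 × 10^9/L from "28 days after ga101 infusion has been completed/stopped" and marks it for BH39147.

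**Schedule.** In Appendices 1 and 2 the last hematology mark is at EOM or EOC, 35 days after last dose. Patients without post-induction treatment have their last count at end of induction (EOI). The post-treatment and survival follow-up columns are blank for hematology. Immunoglobulins and lymphocyte immunophenotyping continue every 3 months, but only until recovery, progression or new treatment.

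**The concern.** The recovery rows otherwise follow a three-month sequence, and one step is absent. A programmer following the template has nowhere to record a month-4 recovery, so the table would understate recovery in its first half-year.

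The second part concerns the data behind the table. The SAP asks for recovery beyond 12 months and for late-onset neutropenia, but the protocol schedules no blood count that could supply either after EOM or EOC. By the SAP's own laboratory grading (6.4), ANC below 1.0 × 10^9/L is Grade 3 or 4. A late-onset case is therefore also a Grade 3 or higher neutropenia, an adverse event of special interest under protocol 5.2.3. Grade 3 and 4 infections are collected for 2 years after obinutuzumab without a scheduled neutrophil count alongside them.

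**Working it through.** The plan gives no figure to reproduce here. The check is one of coverage and timing.

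**1. Coverage of the follow-up axis by Output 55 (months)**

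| Interval | Row with a Yes count |
|---|---|
| 0 to 3 | first row |
| between 3 and 6 | none |
| 6 to 9 | second row |
| 9 to 12 | third row |
| after 12 | fourth row |

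The uncovered length is 6 − 3 = 3 months of the first 12. Month 9 belongs to both the second and third rows. Month 12 belongs only to the third, because the fourth starts after 12.

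**2. The clock.** Output 55 does not define month 0. If follow-up starts as in SAP 2.3.4 (after last dose plus 28 days, assuming no new anti-lymphoma therapy sooner), the post-maintenance visits nominally 3 and 6 months after last dose fall as follows, at 30.4375 days per month:
- 3 × 30.4375 − 28 = 63.3 days = 2.1 months of follow-up
- 6 × 30.4375 − 28 = 154.6 days = 5.1 months of follow-up

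On that clock an unscheduled count taken at the second visit would have no row. On a different clock, or with visits assigned by planned label, the placement changes.

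**3. Scheduled counts inside the late-onset window.** The window opens 28 days after obinutuzumab ends.
- Patients completing maintenance or consolidation: the EOM or EOC count is at day 35, and 35 − 28 = 7 days into the window. No scheduled count follows. This takes the last dose to be the last obinutuzumab infusion.
- Patients with no post-induction treatment: EOI is 6 to 8 weeks after Day 1 of the last cycle, the day of the last infusion. That is day 42 to 56, or 14 to 28 days into the window. Again no scheduled count follows.

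**4. The recovery rule applied to scheduled visits.** Coding the SAP 6.4.3 rule reproduces its four worked examples in order: not recovered, recovered, not recovered, not recovered. A patient below 1.0 at the last visit before end of treatment, at or above 1.0 at EOM or EOC, and with no later count matches the first example and is not recovered. Scheduled visits cannot confirm a recovery first seen at EOM or EOC.

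**5. Effect of adding the row.** The rows then cover 0 to beyond 12 months without a gap. As with the later rows, the new one would hold only unscheduled counts unless hematology is scheduled in follow-up.

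**The case against.** **Whether Output 55 applies.** The SAP is a harmonized document for several studies, to be read with a list of planned outputs that is not available here. Its introduction does not name BH39147, although the 6.2.2 tables have a BH39147 column. Whether this table will be produced for this trial is unconfirmed.

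**Whether the row is really absent.** A row lost when the PDF was read cannot be excluded. The table has other blemishes: an asterisk without a footnote and a stray letter in the last row label. That is a reason to ask the sponsor to confirm, not to drop the point.

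**Size of the loss.** A reader might infer that about half of the 3- and 6-month visits fall in no row. The documents do not support this. No neutrophil count is scheduled at those visits, so no share of scheduled counts can be lost. SAP 2.3.9 also assigns by-visit follow-up data by planned event, not by scattered actual dates.

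**Adding up.** A reader might also infer that the rows should sum to a total and fail to. Nothing says they must, since each has its own Yes, No and n. SAP 6.4.3 separately defines time to recovery in days, so a month-4 recovery is defined but has no Yes count in this table.

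**Reach of the late-onset point.** It would be too broad to say that late-onset neutropenia will be missed generally. The definition is tied to obinutuzumab, so it covers FL patients and the DLBCL escalation patients given obinutuzumab, not the rituximab-treated DLBCL cohorts. One scheduled count does fall in the window. Adverse events are reported to 90 days after last dose, Grade 3 or higher neutropenia is immediately reportable, known Grade 3 or 4 neutropenia is followed until it improves, and related serious events remain reportable afterwards. These safeguards stand. What remains is mainly the asymptomatic case that nobody has reason to test for.

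**Conclusion.** The point holds as a minor one, in two parts.

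First, Output 55 as written cannot count as Yes a recovery first dated between months 3 and 6, and the patient may instead be shown as No. Month 9 is double-assigned. This rests on the template being complete as read and being used for BH39147.

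Second, no hematology is scheduled after EOM or EOC. For obinutuzumab-treated patients who complete post-induction treatment, one count 7 days into the window is the only scheduled look for late-onset neutropenia. Asymptomatic cases after it can be missed, and a recovery first seen at that visit cannot be confirmed under SAP 6.4.3 from scheduled data.

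The number of patients affected cannot be estimated from the documents. The primary endpoint, the sample size and the efficacy analyses are not affected.

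**What to change.** **Output 55.** Confirm whether the missing row was intended. Add a 3 to 6 months row, make the bounds non-overlapping (for example, over 3 to 6, over 6 to 9, over 9 to 12), and state the day from which follow-up months are counted. Bring the footnote into line with SAP 6.4.3 by adding the next-visit confirmation it now omits. Cost: one table row and a few words in the SAP.

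**Schedule, as a cheap improvement.** Add a local blood count at the existing 3-monthly post-treatment follow-up visits for obinutuzumab-treated patients. Do not tie it to the immunoglobulin and immunophenotyping draws, which stop on recovery. Cost: one routine blood test per visit, and a protocol amendment with ethics approval across about 25 sites. It could be carried with the next amendment. If it is not adopted, the report should say that recovery and late-onset neutropenia after EOM or EOC rest on unscheduled counts.

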## 10.56 Output 56 Vital Signs Change from Baseline by Visit

Visit	Group 1 (N=nnn)	
	Value at Visit	Change from Baseline
Baseline		
n	nnn	
Mean (SD)	xx.x (xx.x)	
Median	xx.x	
Min-max	xx.x -xx.x	
Cycle X		
n	nnn	nnn
Mean (SD)	xx.x (xx.x)	xx.x (xx.x)
Median	xx.x	xx.x
Min-max	xx.x-xx.x	xx.x-xx.x

### Programing notes:

1. Analysis population: Safety
2. Template ID: VST01
3. Program name: T\_VS\_CB
4. Analysis variables: Weight, Temperature, Respiratory rate, Pulse, SBP, DBP

## 10.57 Output 57 ECG Results Shift Table

Treatment x (N=xx)

Shift TO: ECG Result at Visit	Shift FROM: Baseline			Total
	Abnormal, clinically significant	Abnormal, not clinically significant	Normal	
END OF INDUCTION COMPLETION / DISCONTINUATION				
Abnormal, clinically significant	0	0	0	0
Abnormal, not clinically significant	0	xx (xx.xx%)	xx (xx.xx%)	xx (xx.xx%)
Normal	0	xx (xx.xx%)	xx (xx.xx%)	xx (xx.xx%)
Total	0	xx (xx.xx%)	xx (xx.xx%)	xx (xx.xx%)
END OF MAINTENANCE COMPLETION / DISCONTINUATION				
Abnormal, clinically significant	0	0	0	0
Abnormal, not clinically significant	0	xx (xx.xx%)	0	xx (xx.xx%)
Normal	0	0	0	0
Total	0	xx (xx.xx%)	0	xx (xx.xx%)

Baseline assessment is the last valid assessment in the 28 day window before first administration of a study treatment component.

Programing notes:

1. Analysis population: Safety
2. Template ID: EGT01
3. Program name: T\_EG\_CB
4. Analysis variables: Electrocardiogram (ECG)

### 10.58 OUTPUT 58 Listing of Time-to-Event Endpoints

Treatment group	CRTN/Pt No.	Overall Survival (months)	PFS (months)	EFS (months)	DFS (months)	Duration of Response (months)
	xxxx/xxxx	xxx	xxx	xxx	xxx	xxx
		xxx	xxx*	xxx*	xxx*	
		xxx	xxx	xxx	xxx	
		xxx	xxx*	xxx*	xxx*	
		xxx	xxx	xxx	xxx	
		xxx	xxx*	xxx*	xxx*	
		xxx	xxx	xxx	xxx	
...						

\* Censored Observation

**Programming Note:**

1. Analysis population: Safety
2. Program name: L\_EF\_TTE
3. Time-to-Event endpoints are consist of overall survival, EFS, PFS, and duration of response.

### 10.59 Output 59 Listing of Tumor Response Assessment

CRTN/PT No.	Cycle	Study Day#	New Lesion	Objective evidence of clinical progression	Response not including PET scan results (IRC)	Response based upon PET-CT scans (IRC)	Response not including PET scan results (Investigator)	Response based upon PET-CT scans (Investigator)
xxxx/xxxx			Yes	Yes				

Response will be determined on the basis of PET-CT scans or CT scans alone, using the modified Lugano 2014 criteria

#: Days from first dose of study medication

Programming Note:

1. Analysis population: Safety
2. Program name: L\_EF\_CONCORD
3. CRF: NHL response assessment and IRC data
4. **Response based upon PET-CT scans include 2 results: using Lugano 2014 criteria and modified Lugano 2014 criteria (follow protocol).**
5. **Study BO29563: response assessment is also using Cheson 2007 criteria.**

Note: It is ok to split the table into two: one for investigator and the other for IRC.

## 10.60 Output 60 CR Rate at End of Induction

	Treatment Group 1 (N=nn)	Treatment Group 2 (N=nn)
Based on Modified LUGANO 2014 - PET-CT		
As Determined by the IRC		
Complete Response (CR)	xxx (xx.x %)	xxx (xx.x %)
90% CI for Response Rates	(xx.x, xx.x)	(xx.x, xx.x)
As Determined by the Investigator		
Complete Response (CR)	xxx (xx.x %)	xxx (xx.x %)
90% CI for Response Rates	(xx.x, xx.x)	(xx.x, xx.x)
Based on LUGANO 2014 - PET		
As Determined by the IRC		
Complete Response (CR)	xxx (xx.x %)	xxx (xx.x %)
90% CI for Response Rates	(xx.x, xx.x)	(xx.x, xx.x)
As Determined by the Investigator		
Complete Response (CR)	xxx (xx.x %)	xxx (xx.x %)
90% CI for Response Rates	(xx.x, xx.x)	(xx.x, xx.x)
Based on Modified CHESON 2007 - CT or MRI		
As Determined by the IRC		
Complete Response (CR)	xxx (xx.x %)	xxx (xx.x %)
90% CI for Response Rates	(xx.x, xx.x)	(xx.x, xx.x)
As Determined by the Investigator		
Complete Response (CR)	xxx (xx.x %)	xxx (xx.x %)
90% CI for Response Rates	(xx.x, xx.x)	(xx.x, xx.x)
Based on Modified CHESON 2007 - CT or MRI and PET		
As Determined by the IRC		
Complete Response (CR)	xxx (xx.x %)	xxx (xx.x %)
90% CI for Response Rates	(xx.x, xx.x)	(xx.x, xx.x)
As Determined by the Investigator		
Complete Response (CR)	xxx (xx.x %)	xxx (xx.x %)
90% CI for Response Rates	(xx.x, xx.x)	(xx.x, xx.x)

90% CI for rates were constructed using Clopper-Pearson method.

Programming Note:

1. Analysis population: Safety
2. Template ID: RSPT01
3. Program name: T\_CRR
4. EOI time window: TBD
5. Some studies may require CR tabulation based on Cheson criteria, Lugana, or modified Lugano, follow SMT instruction.

## 10.61 Output 61 OR Rate at End of Induction

	Treatment Group 1 (N=nn)	Treatment Group 2 (N=nn)
Based on Modified LUGANO 2014 - PET-CT		
As Determined by the IRC		
Objective Response (CR, PR)	xxx (xx.x %)	xxx (xx.x %)
90% CI for Response Rates	(xx.x, xx.x)	(xx.x, xx.x)
As Determined by the Investigator		
Objective Response (CR, PR)	xxx (xx.x %)	xxx (xx.x %)
90% CI for Response Rates	(xx.x, xx.x)	(xx.x, xx.x)
Based on LUGANO 2014 – PET		
As Determined by the IRC		
Objective Response (CR, PR)	xxx (xx.x %)	xxx (xx.x %)
90% CI for Response Rates	(xx.x, xx.x)	(xx.x, xx.x)
As Determined by the Investigator		
Objective Response (CR, PR)	xxx (xx.x %)	xxx (xx.x %)
90% CI for Response Rates	(xx.x, xx.x)	(xx.x, xx.x)
Based on Modified CHESON 2007 - CT or MRI		
As Determined by the IRC		
Objective Response (CR, PR)	xxx (xx.x %)	xxx (xx.x %)
90% CI for Response Rates	(xx.x, xx.x)	(xx.x, xx.x)
As Determined by the Investigator		
Objective Response (CR, PR)	xxx (xx.x %)	xxx (xx.x %)
90% CI for Response Rates	(xx.x, xx.x)	(xx.x, xx.x)
Based on Modified CHESON 2007 - CT or MRI and PET		
As Determined by the IRC		
Objective Response (CR, PR)	xxx (xx.x %)	xxx (xx.x %)
90% CI for Response Rates	(xx.x, xx.x)	(xx.x, xx.x)
As Determined by the Investigator		
Objective Response (CR, PR)	xxx (xx.x %)	xxx (xx.x %)
90% CI for Response Rates	(xx.x, xx.x)	(xx.x, xx.x)

90% CI for rates were constructed using Clopper-Pearson method.

Programming Note:

1. Analysis population: Safety
2. Template ID: RSPT01

3. Program name: T\_ORR
4. EOI time window: TBD

## 10.62 Output 62 CR Rate at 12 Months after Initiation of Induction

	Treatment Group 1 (N=nn)	Treatment Group 2 (N=nn)
Based on PET-CT as Determined by the IRC using Lugano 2014 Criteria		
Complete Response (CR)	xxx (xx.x %)	xxx (xx.x %)
90% CI for Response Rates	(xx.x, xx.x)	(xx.x, xx.x)
Based on PET-CT as Determined by the Investigator using Lugano 2014 Criteria		
Complete Response (CR)	xxx (xx.x %)	xxx (xx.x %)
90% CI for Response Rates	(xx.x, xx.x)	(xx.x, xx.x)
Based on PET-CT as Determined by the IRC using modified Lugano 2014 Criteria		
Complete Response (CR)	xxx (xx.x %)	xxx (xx.x %)
90% CI for Response Rates	(xx.x, xx.x)	(xx.x, xx.x)
Based on PET-CT as Determined by the Investigator using modified Lugano 2014 Criteria		
Complete Response (CR)	xxx (xx.x %)	xxx (xx.x %)
90% CI for Response Rates	(xx.x, xx.x)	(xx.x, xx.x)
Based on CT alone as Determined by the IRC		
Complete Response (CR)	xxx (xx.x %)	xxx (xx.x %)
90% CI for Response Rates	(xx.x, xx.x)	(xx.x, xx.x)
Based on CT alone as Determined by the Investigator		
Complete Response (CR)	xxx (xx.x %)	xxx (xx.x %)
90% CI for Response Rates	(xx.x, xx.x)	(xx.x, xx.x)

90% CI for rates were constructed using Clopper-Pearson method.

Programming Note:

1. Analysis population: Safety
2. Template ID: RSPT01
3. Program name: T\_CRR12
4. **Patient subset: Patients who have positive PET scans (CR/PR) at EOI**

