### **6.5.3 Exploratory Efficacy Endpoints**

Exploratory efficacy analyses will include an estimation of the proportion of patients achieving the following endpoint:

- For patients who have positive PET scans at EOI:
  - CR at 12 months, as determined by the IRC and by the investigator on the basis of PET-CT scans in patients with FL
  - CR at EOC, as determined by the IRC and by the investigator on the basis of PET-CT scans, in patients with DLBCL

Additional descriptive analysis based on TP53 mutation status will be performed on the following endpoint:

- CR at the EOI, as determined by the IRC on the basis of PET-CT scans

Point estimates will be presented, along with the corresponding two-sided 90% Clopper-Pearson exact CIs. Patients without a post-baseline tumor assessment will be considered non-responders.

Exploratory efficacy analyses will also be performed on the following endpoints (see definitions in Section [2.2.3](#)):

- PFS
- EFS
- DFS
- OS

PFS, EFS, DFS, and OS will be summarized descriptively using the Kaplan-Meier method ([Kaplan and Meier 1958](#)). For the PFS, EFS, and DFS analyses, data for patients without an event of interest will be censored at the date of the last tumor assessment. For patients without post-baseline tumor assessments, data will be censored at the date of initiation of study treatment plus 1. For the OS analysis, data for

patients who have not died will be censored at the date the patient was last known to be alive. When medians are reached, the corresponding estimated median will be provided, along with the 95% CI using the method of [Brookmeyer and Crowley \(1982\)](#). In addition, estimates of the proportion of patients who are event free at 6 months, 9 months, 1 year, and 2 years will be provided, along with 95% asymptotic CIs using Greenwood's formula for standard errors.

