## Appendix 4 Lugano Response Criteria for Malignant Lymphoma (Cheson et al. 2014)

In this study, the designation of a complete response (CR) using positron emission tomography–computed tomography (PET-CT)–based response requires normal bone marrow by morphology for patients with bone marrow involvement at baseline. If indeterminate by morphology, immunohistochemistry must be negative. Additionally, designation of PET-CT–based partial response (PR) requires that computed tomography (CT)-based response criteria for a CR or a PR be met in addition to the PET-CT–based response criteria for a PR.

Revised Criteria for Response Assessment		
Response and Site	PET-CT–Based Response	CT-Based Response
Complete	Complete metabolic response	Complete radiologic response (all of the following)
Lymph nodes and extralymphatic sites	Score 1, 2, or 3 a with or without a residual mass on 5PS b It is recognized that in Waldeyer’s ring or extranodal sites with high physiologic uptake or with activation within spleen or marrow (e.g., with chemotherapy or myeloid colony-stimulating factors), uptake may be greater than normal mediastinum and/or liver. In this circumstance, complete metabolic response may be inferred if uptake at sites of initial involvement is no greater than surrounding normal tissue even if the tissue has high physiologic uptake.	Target nodes/nodal masses must regress to $\leq 1.5$ cm in LDi No extralymphatic sites of disease
Non-measured lesion	Not applicable	Absent
Organ enlargement	Not applicable	Regress to normal
New lesions	None	None
Bone marrow	No evidence of FDG-avid disease in marrow	Normal by morphology; if indeterminate, IHC negative

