## Appendix 4 Lugano Response Criteria for Malignant Lymphoma (Cheson et al. 2014) (cont.)

Revised Criteria for Response Assessment		
Response and Site	PET-CT–Based Response	CT-Based Response
Partial	Partial metabolic response	Partial remission (all of the following)
Lymph nodes and extralymphatic sites	Score 4 or 5 b with reduced uptake compared with baseline and residual mass(es) of any size	≥ 50% decrease in the sum of the product of the diameters SPD of up to 6 target measurable nodes and extranodal sites
	At interim, these findings suggest responding disease	When a lesion is too small to measure on CT, assign 5 mm × 5 mm as the default value
	At end of treatment, these findings indicate residual disease	When no longer visible, 0 × 0 mm
		For a node > 5 mm × 5 mm, but smaller than normal, use actual measurement for calculation
Non-measured lesion	Not applicable	Absent/normal, regressed, but no increase
Organ enlargement	Not applicable	Spleen must have regressed by > 50% in length beyond normal
New lesions	None	None
Bone marrow	Residual uptake higher than uptake in normal marrow but reduced compared with baseline (diffuse uptake compatible with reactive changes from chemotherapy allowed). If there are persistent focal changes in the marrow in the context of a nodal response, consideration should be given to further evaluation with MRI or biopsy or an interval scan.	Not applicable

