### 5.3 Analysis of Exploratory Endpoints

Exploratory efficacy analyses will include estimation of the proportion of patients achieving each of the following endpoints:

- For patients who have positive PET scans at EOI: CR at 12 months, as determined by the IRC and by the investigator on the basis of PET-CT scans
- CR at 12 months, as determined by the investigator on the basis of CT scans alone (BO29561)
- CR at 12, 24, and 30 months in patients with previously untreated FL, as determined by the investigator using modified Cheson 2007 criteria (BO29563)
- Additional descriptive analysis based on TP53 status will be performed on the following endpoint: CR at EOI, as determined by the IRC on the basis of PET-CT scans (BH29812)

Point estimates will be presented, along with the corresponding two-sided 90% Clopper-Pearson exact CIs. Patients without a post-baseline tumor assessment will be considered non-CRs and non-responders, respectively.

Exploratory efficacy analyses will also be performed on the following endpoints:

- PFS, defined as the time from initiation of study treatment to first occurrence of disease progression or relapse, as determined by investigator on the basis of CT scans alone, or death from any cause
- EFS, defined as the time from initiation of study treatment to any treatment failure, including disease progression or relapse, as determined by investigator on the basis of CT scans alone, initiation of new anti-lymphoma therapy, or death from any cause, whichever occurs first
- DFS, defined, among patients achieving a CR, as the time from the first occurrence of a documented CR to relapse, as determined by the investigator on the basis of CT scans alone, or death from any cause, whichever occurs first
- DOR, defined as the time from the initial response to disease progression or death among patients who have experienced a CR or PR during study (Study BO29561/BO29562).
- OS, defined as the time from initiation of study treatment to death from any cause

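### SAP Output 62 limits the 12-month CR table to PET-positive patients labelled CR/PR, which is not the protocol's PET-positive subset

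*SAP*

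**What the plan says.** **The subset.** SAP 10.62 (Output 62), programming note 4, sets it as "Patients who have positive PET scans (CR/PR) at EOI". Protocol 6.5.3 says "For patients who have positive PET scans at EOI", and protocol 2.2.3 agrees. Both then list two rates, each by independent review committee (IRC) and by investigator: CR at 12 months in follicular lymphoma (FL), and CR at end of consolidation (EOC) in DLBCL. SAP 5.3 says "For patients who have positive PET scans at EOI: CR at 12 months" and does not mention EOC.

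**What a positive PET is.** Neither document defines it formally, but protocol Appendix 4 gives the substance.
- CR is a complete metabolic response: score 1 to 3 and no FDG-avid marrow disease. At sites of high physiologic uptake, "complete metabolic response may be inferred if uptake at sites of initial involvement is no greater than surrounding normal tissue".
- The modified CR used in this trial also "requires normal bone marrow by morphology for patients with bone marrow involvement at baseline".
- Partial metabolic response is score 4 or 5 with reduced uptake. Of this Appendix 4 says: "At end of treatment, these findings indicate residual disease". In marrow it is "Residual uptake higher than uptake in normal marrow but reduced compared with baseline".
- No metabolic response and progressive metabolic disease also carry score 4 or 5, or new avid foci for progression.

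**When the later scan is done.** In FL, the 12-month PET-CT is scheduled only when the EOI PET-CT is positive (Appendix 1, footnote gg). In DLBCL, the EOC PET-CT has the same condition (Appendix 2, footnote oo), and the EOC visit applies to patients who complete or stop consolidation (footnote b). Only patients in CR or PR at EOI go on to maintenance or consolidation (protocol 3.1.3).

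**Missing data.** SAP 5.3: "Patients without a post-baseline tumor assessment will be considered non-CRs and non-responders, respectively". Protocol 6.5.3 has the same rule in substance.

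**The concern.** The endpoint asks how many patients who still have avid disease after induction reach CR later. The programmer works from the output note, and the note adds a response category found nowhere in the endpoint's definition. One of the two categories it names, CR, cannot be PET-positive. The note can be read in two ways, and neither gives the protocol's denominator.

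Two related gaps affect the same analysis. First, the missing-data rule covers only patients with no post-baseline assessment at all. A PET-positive patient with stable or progressive disease (SD/PD) has an EOI scan, does not enter maintenance or consolidation, and may never have the later PET-CT; no rule says how that patient counts. Second, the DLBCL endpoint, CR at EOC, is not named in SAP 5.3 and has no table in the SAP's output list.

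At stake is one exploratory rate per disease, reported under the protocol's label for a different set of patients.

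**Working it through.** The documents give no figure for this subset, so there is nothing to reproduce. The check is a comparison of definitions, followed by an illustration of size.

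**Who is in the denominator**

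| EOI PET-CT category (Appendix 4) | PET-positive | Protocol 6.5.3, SAP 5.3 | Output 62 read as CR or PR | Output 62 read as PET-positive and CR/PR |
|---|---|---|---|---|
| CR | no | out | in | out |
| PR | yes | in | in | in |
| No metabolic response | yes | in | out | out |
| Progression | yes | in | out | out |

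The protocol's set and the CR-or-PR set share only the PRs.

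Output 62 also has CT-alone rows. FL patients in maintenance have a 12-month CT (Appendix 1, footnote jj), so under the CR-or-PR reading EOI complete responders would fill those rows with real data although they are outside the endpoint.

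**Inputs for the illustration (FL)**
- From protocol 6.1.2: n = 40 and a planning CR rate of 55%, so 0.55 × 40 = 22 CR at EOI.
- Not CR: 40 − 22 = 18. This is an upper bound for PET-positive, because a patient can miss the modified CR on marrow morphology alone, or have no EOI PET.
- Assumed, not in the documents: all 18 are PET-positive; 8 are PR (range 4 to 14); 3 convert to CR by 12 months.

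The rate is x/n. The 90% Clopper-Pearson limits are the 0.05 quantile of Beta(x, n − x + 1) and the 0.95 quantile of Beta(x + 1, n − x).

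| Denominator | 4 PRs | 8 PRs | 14 PRs |
|---|---|---|---|
| Protocol: PET-positive | 3/18 = 16.7% (4.7, 37.7) | same | same |
| CR or PR; EOI CRs without a 12-month PET-CT count as non-CR | 3/26 = 11.5% (3.2, 27.2) | 3/30 = 10.0% (2.8, 23.9) | 3/36 = 8.3% (2.3, 20.2) |
| CR or PR; EOI CRs carried as CR (22 + 3 = 25) | 25/26 = 96.2% (83.0, 99.8) | 25/30 = 83.3% (68.1, 93.2) | 25/36 = 69.4% (54.5, 81.8) |
| PET-positive PRs only | 3/4 = 75.0% (24.9, 98.7) | 3/8 = 37.5% (11.1, 71.1) | 3/14 = 21.4% (6.1, 46.6) |

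In the CR-or-PR set, EOI complete responders make up 22/26 = 85%, 22/30 = 73% and 22/36 = 61%. Either reading drops 18 − 4 = 14, 18 − 8 = 10 or 18 − 14 = 4 of the PET-positive patients.

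With 4 conversions instead of 3, and 8 PRs, the four rates are 4/18 = 22%, 4/30 = 13%, 26/30 = 87% and 4/8 = 50%. The pattern is the same.

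**The case against.** The best defence is that the note means PET-positive patients in response, that is, PET-CT partial responders. This has support. Protocol 4.5.5 requires a CT-based CR or PR for a PET-CT PR, which could explain the parenthesis. The FL 12-month PET-CT sits in the maintenance column of Appendix 1 and is timed to a treatment administration. Only CR or PR patients get maintenance, and patients who progress move to survival follow-up. PET-positive PRs are therefore, in practice, the FL patients with a scheduled 12-month scan.

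That explains the note but does not make it the protocol's endpoint. The protocol does not exclude PET-positive SD/PD patients. Leaving them out, rather than counting them as not converted, raises the rate in every column above. Conversion among partial responders is a legitimate quantity, but a different one, and it would have to be stated.

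Other points stand in part.
- The 83% figure needs EOI complete responders to be carried forward as CR, which no text provides for. It is one end of a range, not a prediction.
- The PR count and the conversions are assumptions, so the figures show sensitivity, not a measured effect.
- The SAP is a multi-study template. Its introduction does not list BH39147, although its adverse-event tables in 6.2.2 have a column for it, and the separate list of planned outputs is not available. This limits the impact but does not remove the error in the note.
- The missing-scan rule and the EOC endpoint do not follow from the parenthesis. They are separate gaps in the same analysis.

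**Conclusion.** The concern holds and is minor. As written, Output 62 would not report the rate defined in protocol 6.5.3 and SAP 5.3.

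The direction of the error depends on the reading. Against 17% for the protocol's subset, the illustration gives 10% if EOI complete responders enter and count as non-CR, 83% if they enter and are carried as CR, and 38% if only PET-positive PRs are kept. These rest on the protocol's 55% of 40 and on the assumed 8 PRs and 3 conversions. The mismatch in definitions rests on none of these assumptions. It rests only on reading a complete metabolic response as PET-negative, which Appendix 4 supports.

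The endpoint is exploratory. Neither the primary analysis nor the secondary response rates use this subset.

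**What to change.** 1. Delete the CR/PR parenthesis from the Output 62 note and, for this trial, limit the 12-month table to FL.
2. Define the subset as patients whose EOI PET-CT is evaluable and not a complete metabolic response under Appendix 4, using the IRC's reading for the IRC rate and the investigator's for the investigator rate. This takes in residual avid marrow disease and new avid foci. A bare 5-point cut would not do, because Appendix 4 allows a complete metabolic response to be inferred at physiologic sites and judges marrow separately.
3. The unmodified Lugano 2014 PET-CT category (PR, no metabolic response or progression) gives this subset. It leaves out patients who miss the modified CR only on marrow morphology, and patients with no EOI PET.
4. Count PET-positive patients without the later PET-CT (12 months in FL, EOC in DLBCL) as non-CR, including SD/PD patients who do not enter maintenance or consolidation, and show their number. If conversion among PET-positive PRs is also wanted, report it as a separate, labelled rate.
5. Add CR at EOC among EOI PET-positive DLBCL patients to SAP 5.3 and to the outputs.

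The cost is one parenthesis, a few SAP lines and one DLBCL table. SAP Output 59, note 4, already lists both the unmodified and the modified Lugano results, subject to the protocol. If this trial captures only the modified result, the assessor's EOI PET reading must also be taken from the response data.
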